### 2.2. Continuous outcomes (if any) – not applicable

**We have none. This section is not developed.**

### **2.3 Secondary analysis: Time to event (Aim 2)**

As a secondary outcome, and to confirm that statistical significance from our primary analysis applies equally to time to event data, we will use stratified (by practice site) time-to-event analysis for receipt of vaccine.

Our goal will be to use, where possible, assumption free methods and avoid parametric approaches, and at the same time to present results in a format that can be interpreted easily to a clinical audience. For these reasons, we are deliberately avoiding traditional approaches such as Cox regression and common metrics such as hazard ratios.

This section covers two separate topics:

First, in keeping with our goal of using assumption-free, randomization-test based methods, we shall apply this approach to time-to-event analyses.

Second, we shall estimate restricted mean survival times to arrive at more meaningful estimate of time to event and to avoid "hazard ratios"

#### **2.3.1 Time zero**

Time zero for all time to event analyses is the date of child's initial vaccine dose.

#### **2.3.2 Descriptive Kaplan-Meier (KM) curves of time from 1st to 2nd dose**

Non parametric Kaplan-Meier curves:

Stata: "sts graph"

These will be done with censoring date April 30 (primary) and day 42 (secondary). Both analyses will be reported and plotted

We will use inverted KM curves. This graphical approach will be our primary analysis. Log rank tests will generate p-values if proportional hazards assumption met. Stratification will be by clinic site.

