## Flu2Text: A Multi-Site Study assessing an Intervention for 2nd Dose of Influenza Vaccine

### Overview of the study

This study will assess the impact of text message reminders on the receipt of the second dose of influenza vaccine and will take place in 40-50 practices over two influenza seasons.

This study includes a sample of up to 4,000 parents over the course of two flu seasons (up to approximately 40-250 parents any of 40-50 sites per influenza season). Eligible parents will have a child who received their first vaccine dose and are in need of 2 doses that season. The study will include parents who have a 6-month through 8-year-old child (or a child who is of the age that necessitates 2 doses, should age recommendations change as determined by the CDC) who received their first vaccine dose and is in need of 2 doses that season. Current recommendations require 2 doses for certain children 6 months through 8 years old.

Within each practice site, parents will be randomized to receive either:

- 1) a series of text message reminders embedded with influenza vaccine health-literacy promoting information, or
- 2) usual care

- *Season 1 (2017-2018):* usual care alone
- *Season 2 (2018-2019):* usual care plus a text message containing a link to health and parenting information from the American Academy of Pediatrics website

The primary outcome will be receipt of two doses of influenza vaccine by the end of the season (April 30). A secondary outcome will be timeliness of receipt of 2nd dose.

The study will be conducted over the 1st season (September 2017–April 2018) as an effectiveness trial and the 2nd season (July 2018–April 2019) as a replication study to validate the approach and allow refinement based on parent and practice feedback. The intervention targets the parent-child dyad.

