### Background

Influenza, as evidenced by seasonal epidemics, remains a significant and largely preventable source of morbidity and mortality resulting in an estimated 31 million outpatient visits, 226,000 hospitalizations, and 3,000 to 49,000 deaths annually (depending on the virulence of the circulating strain), along with a high cost burden from direct medical expenses and days lost from work. Young children, the focus of this proposal, are at especially high risk for hospitalization and serious influenza complications including pneumonia and neurological outcomes like seizures and encephalopathy. They are also a source of transmission to other high-risk household members. However, influenza vaccine coverage is low. Only 58.9% of U.S. children 6 months to 17 years-old receive at least one needed influenza dose annually. Young children <9 years are at particular risk for under vaccination because they require 2 doses at least 4 weeks apart in the first influenza season they are vaccinated, since one dose does not confer adequate influenza protection; some previously vaccinated children also require 2 doses in subsequent seasons depending on their previous influenza vaccinations. Even among those who need two doses in a given season and who receive the first dose, only 40-60% receive the second dose.

Timeliness is also key, as children are not fully protected until two weeks after receiving the second dose, many children do not receive this second dose close to 4 weeks after the first, as recommended. This delay leaves many children unprotected when influenza virus begins circulating. Increasing timely receipt of second doses is also a worthwhile focus as parents (meaning the adult in a parenting role, including guardians) have already “accepted” vaccination as evidenced by their child receiving the first dose.

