#### ***Study Intervention: Text Messages***

Messages will be sent in English or Spanish based on parent preference.

Using date of initial vaccine as day 0, text messages will be sent to all parents randomized to the intervention on the following days:

- Day 14: notifying parents that their child is in need of a second flu shot.
- Day 21: educational text messages, with interactivity, through which parents can select to receive more information via text message.
- Day 25: letting parents know when and where they will need to go to receive the second shot
- Day 28 (day vaccine is due): it is now time to take [child] to be vaccinated (2nd flu shot).
- Day 42 (2 weeks after it is due): another interactive message will assess potential vaccine barriers and offer selected responses.

Texts will stop after day 42. We will not be able to know from the practices in time to stop messages after a child was vaccinated. However, as the shot is not due until day 28, it would likely only be the day 42 message that could come after the child was vaccinated. That message has been worded to first assess whether the child received the vaccine.

**Dates of influenza vaccinations and related visit dates:** Dates of influenza vaccinations and related visit dates will be collected from the practices. The part of the Patient Enrollment/Outcomes Forms that stays with the site will have child's first and last name and date of birth. The site will use this to identify the medical record, extract relevant influenza vaccination dates and related visit dates and transfer this information to the research team. Practices will do this by using their medical records and/or by checking their city or state immunization registry should the practice have no record of receipt of subsequent influenza doses for the current season.

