### 2.0.1 Analyses will proceed separately by season

Seasons 1 and 2 will be analyzed separately.

Secondary analysis will combine seasons, adjusting for season as a stratifying factor. Site will be considered to be a separate stratum by season.

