### 2.3.4 Risk difference (of completion of vaccine series) as of a given time

The purpose of this analysis is to re-express the results of Kaplan Meier survival estimates to generate more interpretable results. It is therefore an alternative method to express the results and will not be considered as a multiple test in need of adjusting confidence intervals. This analysis is not separate from the Kaplan Meier analysis. Rather it only quantifies the values of the two curves (y) at a given value of time (e.g. 42 days). This is therefore, just a re-expression of the Kaplan Meier plot.

Use of pseudo-observation approach with syntax:

```
Stpsurv, at(time1) failure after(time0),
```

Where time(1) can be as of day 42, 60, and 90.

As April 30 does not account for different days of follow up per child, it will not be possible to use that date for analysis. Programming details appear in Stata program “stpm2” (Lambert, Andersson, Royston).

Syntax is (approximately):

```
standsurv, at1(treatment 0) at2(treatment 1) timevar(timevar) ci  
contrast(difference)
```

See stpm2 syntax for “standsurv”

“ci” refers to cumulative incidence

“timevar” needs to take on the value 42, 60 and 90

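### SAP 2.3.2 makes the log-rank p-value depend on proportional hazards, which the test does not need, and 2.3.4 names two routes for one set of risk differences

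*Combined protocol and SAP*

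**What the plan says.** Section 2.3.2 makes the inverted Kaplan-Meier (KM) curves, stratified by clinic site, the main time-to-event display. Of the curves it says "These will be done with censoring date April 30 (primary) and day 42 (secondary"), and of the test: "Log rank tests will generate p-values if proportional hazards assumption met". It does not say how proportional hazards (PH) will be checked, at what threshold, or which p-value replaces the log-rank if the check fails.

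Section 2.3 gives the time-to-event work the job "to confirm that statistical significance from our primary analysis applies equally to time to event data". The same section prefers assumption-free methods and sets Cox regression and hazard ratios aside. Section 2.3.3 runs strbee on a site-stratified log-rank statistic with no PH condition. Section 2.0.1 adds "Seasons 1 and 2 will be analyzed separately", and the protocol overview describes season 2 "as a replication study to validate the approach".

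Section 2.3.4 presents risk differences at days 42, 60 and 90 as nothing more than the heights of the two KM curves. On that ground the analysis "will not be considered as a multiple test in need of adjusting confidence intervals". It first names pseudo-observations (stpsurv). It then points to stpm2 and gives standsurv syntax, marked as approximate and without a model statement. It does not say which of the two supplies the reported figure.

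**The concern.** The log-rank statistic tests equality of the two curves. If that null is true the hazards are equal, and so proportional, whatever their shape over time. PH matters for the power of the test and for reading a single hazard ratio, and this plan reports no hazard ratio. The condition is therefore an unneeded pre-test that uses outcomes by arm, and its form is left open until the data are in hand.

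A changing effect is plausible here. The reminders run from day 14 and "Texts will stop after day 42", so an effect concentrated around the due date at day 28 is a natural expectation. Such an effect is also the kind that a PH check tends to flag. Because each season is analysed on its own, one season could end with a log-rank p-value and its replication without one, even if the true effect is the same.

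In 2.3.4, the case for not adjusting rests on the figures being the KM values in another form. Pseudo-observations satisfy that. A fitted parametric model need not, and its figures could disagree with the curve printed beside them.

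**Working it through.** The plan gives no power, event or hazard figure for this analysis, so there is nothing of its own to reproduce. The check is by reasoning and by simulation under stated assumptions.

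**1. Inputs from the documents.** 1:1 allocation; 40–50 sites; up to 4,000 parents over two seasons, so 2,000 per season was taken as the upper case; 84–90% of children observable to day 90 (SAP 2.3.5). For control completion the Background says that among children "who receive the first dose, only 40-60% receive the second dose".

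**2. Assumed inputs.** Second-dose hazard zero before day 28, h1 on days 28–49, h2 afterwards. Two shapes were each solved for 40%, 50% and 60% control completion by April 30: h1 = 0.02/day with h2 = 0.0010, 0.0031, 0.0058; and h2 = 0.3·h1 with h1 = 0.0104, 0.0144, 0.0196. Windows: 13% uniform on 20–90 days, the rest uniform on 90–230. 45 sites, log-normal site effect with SD 0.3. N = 1,000 or 2,000 per season; 1,500 simulated seasons per scenario, 3,000 for the null.

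**3. Statistics.** Log-rank: U = Σ(d₁ⱼ − dⱼ·r₁ⱼ/rⱼ), Z = U/√V, summed over sites. PH check (assumed, since none is named): score test of treatment × g(time) at 5%, with g the event rank, and log and identity time as alternatives.

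**4. Level under the null, April 30 analysis.** Unconditional: 4.4–5.5%. Among seasons that pass the PH check: 4.3–5.5%. With day-42 censoring, unconditional: 4.2–5.7%. A smaller site-stratified repeat (600 runs per setting) gave 4.5–6.3%, and the same among seasons passing. The condition does nothing for type I error.

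**5. Share of seasons with the p-value withheld, April 30 analysis.**

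| Assumed effect on the hazard | N = 1,000 | N = 2,000 |
|---|---|---|
| ×1.3 on days 28–49 only | 8–27% | 10–49% |
| ×1.5 on days 28–49 only | 13–49% | 19–80% |

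If ×1.3 falls to ×1.15 and persists, the share is 6–15%. If ×1.3 is constant it is 4–6%, and with day-42 censoring it is also 4–6%. The choice of check can matter: with 40% completion, ×1.5 and N = 2,000, the same seasons fail 19% of the time on rank time and 36% on log time. That contrast appears in only one of the two hazard shapes.

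**6. One season with a p-value, the other without.** If each season fails with probability q, the chance is 2q(1 − q):
- q = 0.05 (PH true): 2 × 0.05 × 0.95 = 0.095, or 9.5%.
- q = 0.08: 2 × 0.08 × 0.92 = 0.147, or 15%.
- q = 0.49: 2 × 0.49 × 0.51 = 0.50, or 50%.

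**7. A second simulation with another hazard pattern** (unstratified log-rank, 4,000 trials per scenario, hazard ratio 1.45 on days 28–56 and 1.0 after). Null size was 4.7% with 500 per arm and 5.1% with 1,000 per arm. With the early effect, the test rejects in 80% and 98% of trials. The p-value is withheld in 33% and 60%, so a rejection is reported in only 54% and 40%.

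**8. The two routes in 2.3.4.** 40,000 simulated children in each of 30 settings (3 completion levels × 2 hazard shapes × 5 effect patterns). Pseudo-observation and KM differences agreed to 0.1 point in all 30. A spline model for the log cumulative hazard, with treatment not varying over time, compares as follows at day 42:
- constant effect: within 0.4 point of the true difference;
- ×1.3 falling to ×1.15: 0.6–1.8 points below KM;
- ×1.3 fading: 1.6–2.5 points below KM;
- ×1.5 fading: 2.3–4.4 points below KM.

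With a fading effect, the model is 1.7–3.7 points below KM at day 60 and between 1.5 below and 0.6 above at day 90. With a time-varying treatment term, day 42 is within 0.9 point of KM. The early-effect pattern of step 7, at 200,000 per arm and with one constant hazard ratio fitted, gave KM against model differences of 9.1 against 6.0 points (day 42), 10.2 against 7.2 (day 60) and 8.6 against 8.4 (day 90). Under true PH the two agreed within 0.1 point.

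**The case against.** The strongest reply is that little is lost. The analysis is secondary, the SAP puts estimates and confidence bounds ahead of p-values, and the graph is the main display. RMST (2.3.5) already gives a PH-free estimate, and strbee (2.3.3) inverts a site-stratified log-rank statistic with no PH condition. The confirming role in 2.3 belongs to the time-to-event analysis as a whole, not to this one p-value. All of this stands, and it keeps the stakes low.

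Null simulations cannot show every purpose of the condition. The authors may have wanted to avoid summarising crossing curves with one p-value. That is a legitimate reporting preference, but the curves and RMST already serve it, and it would still need a named check. It does not make the log-rank p-value invalid.

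The withholding rates rest on assumed hazards, and the large ones need an effect confined to the first weeks after the due date. That is right: the rates show direction and range and are not forecasts. The argument about validity does not depend on them.

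On 2.3.4, standsurv can be read as loose programming detail for the pseudo-observation approach, and the SAP allows software to change. But stpm2 is a different, parametric estimator, so the text should say so. The gap depends on a model that the plan does not write out. It is also modest beside sampling error: with 500 per arm and completion of 15–50% (assumed), the 95% half-width is 1.96·√(2p(1 − p)/500), about 4.4–6.2 points. Day 42 has its own Mantel-Haenszel comparison in any case.

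**Conclusion.** Both points hold, as an optional improvement. The PH condition in 2.3.2 is unnecessary for validity, undefined in practice, and out of step with 2.3.3 and with the section's own preference for assumption-free methods. It costs little if the effect is constant (about 5% of seasons lose the p-value). It could cost 8–49% of seasons at N = 1,000 if the effect fades after about day 49, under the assumed hazards and an assumed PH check.

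The 2.3.4 ambiguity is the lesser point. It matters only if the parametric model is the route reported and its treatment effect is held constant over time. The primary April 30 binary outcome, the day-42 Mantel-Haenszel comparison and RMST are unaffected.

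**What to change.** In 2.3.2, delete the PH condition and always report the site-stratified log-rank p-value for both censoring dates, in each season, beside the planned RMST results.

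In 2.3.4, state that the reported day 42, 60 and 90 differences come from the KM curves or from the pseudo-observations already named. If stpm2/standsurv is kept, label it a model-based sensitivity analysis, write out the model, and let the treatment effect vary with time.

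The cost is two wording changes, entered as a dated amendment under section 5.0. No new data and no new primary analysis are needed.

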#### **2.3.3 Stratified randomization test based estimates - confirmatory**

Randomization-based estimates are now available for stratified data in Stata with the program strbee (White 2002). Later versions support stratification. These are iterative, grid search based estimates for inverting the test statistic.

In Stata: Must download latest version using "net search strbee"

The key is the use of "strata()" command below. Then the syntax is:

```
Stset timevar, failure(failure_indicator)
```

```
Strbee treat_var, test(logrank) endstudy(time_to_end_study_var) strata(site)  
adjvars(covariates)
```

### 2.3.4 Risk difference (of completion of vaccine series) as of a given time

The purpose of this analysis is to re-express the results of Kaplan Meier survival estimates to generate more interpretable results. It is therefore an alternative method to express the results and will not be considered as a multiple test in need of adjusting confidence intervals. This analysis is not separate from the Kaplan Meier analysis. Rather it only quantifies the values of the two curves (y) at a given value of time (e.g. 42 days). This is therefore, just a re-expression of the Kaplan Meier plot.

Use of pseudo-observation approach with syntax:

```
Stpsurv, at(time1) failure after(time0),
```

Where time(1) can be as of day 42, 60, and 90.

As April 30 does not account for different days of follow up per child, it will not be possible to use that date for analysis. Programming details appear in Stata program “stpm2” (Lambert, Andersson, Royston).

Syntax is (approximately):

```
standsurv, at1(treatment 0) at2(treatment 1) timevar(timevar) ci  
contrast(difference)
```

See stpm2 syntax for “standsurv”

“ci” refers to cumulative incidence

“timevar” needs to take on the value 42, 60 and 90

### 2.3.5 Restricted mean survival curves (RMST)

RMST will not be a primary analysis, and we will not consider it to be a separate look at the data. Rather, it is another method of reporting the data, and we will not adjust confidence bounds for multiple comparisons.

We will implement restricted mean survival time analysis to compare intervention versus usual care groups (if needed, after adjusting for covariates that are not balanced

between groups) and to arrive at meaningful estimates that do not require proportional hazards assumptions.

We have moved beyond hazard ratios because of the assumptions underlying Cox models and the shortcoming of interpretations (Hernan 2010). If we set a truncation time (Day 42), then RMST has the interpretation "if we follow children for 42 days, they will receive the second vaccine on average by day X" (Royston 2011, 2013). Estimation of between group differences are also possible. The more theoretical interpretation is the area under the survivor function until the time of truncation.

Preiminary analysis of available time per child (analysis blinded to outcome and to the treatment assignment) showed that between 84% and 90% (depending on season) of children has observation windows that extended to day 90 from date of first dose.

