### 3.1.1 Estimating within site effects of subgroups

The within-site effect modification estimate represents the difference in treatment effects across levels of the effect modifier contrasted within (rather than across) sites. For this estimate we shall first use a linear fixed effects model, as implemented in Stata command “*xtreg,fe*”, assuming that the outcome will lie in the probability range of 0.2 and 0.8.

This approach will be a first estimate to be followed by the decomposition approach in section 3.1.2.

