### **3.1.2 Parametric subgroup analysis – decomposing the within and across site effects**

We assume that absolute rates (risks) of second vaccine will not lie at the ends of the interval [0,1]. If that is the case, then we can estimate risk differences with subgroups and then across subgroups in the following 3-step process.

**Step 1:** Using a generalized linear effects, create a site-level variable that equals the mean rate of the group at the site. If at one site, for example, 20% of the children have a chronic medical condition, then create a factor =0.2 for that site (called group\_bar).

**Step 2:** Specify a generalized linear model with the following covariates where treatment and group are 0/1 factors:

Treatment + group + treatment\*group + group\_bar + treatment\*group\_bar + covariates.

This model will decompose the within-site effect of treatment by group and the across-site effect of treatment by group.

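### SAP 2.3.5 reads RMST(42) as the average day by which children receive the second dose; it is the mean number of days without a second dose in the first 42 days

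*Combined protocol and SAP*

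**What the plan says.** Section 2.3 of the SAP (time to event, Aim 2) sets aside Cox regression and hazard ratios in favour of results that a clinical audience can read easily. It states that "we shall estimate restricted mean survival times to arrive at more meaningful estimate of time to event". Section 2.3.5 then gives the plain-language reading at a truncation time of 42 days: "if we follow children for 42 days, they will receive the second vaccine on average by day X". The paragraph closes with a second description, the "area under the survivor function until the time of truncation", which it presents as the more theoretical of the two. Section 2.3.5.1 prespecifies tau at 42, 60 and 90 days, and section 2.3.1 starts the clock at the first dose. Section 2.3.5 says that RMST is not a primary analysis.

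On uptake, the protocol Background reports that, among children who need two doses and have had the first, "only 40-60% receive the second dose", and that many of those second doses are not given close to four weeks after the first.

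**The concern.** The two descriptions in section 2.3.5 are not the same quantity. The area under the survival curve is a mean in which every child counts, including those never vaccinated, who enter at the value tau. A statement that children receive the dose on average by day X implies that they do receive it and that X is a date. When a large share has no second dose by tau, neither is true.

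Ease of interpretation is the stated reason for using RMST, so the plain-language sentence is the part most likely to reach a results table or abstract. Copied there, it would give a false statement about timeliness: a day of receipt for a group in which many children had no receipt. The same label could also pass to the RMST subgroup results in section 3.2.

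**Working it through.** The documents give no RMST value to reproduce, so the check is from the definition.

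**Definition.** Let T be days from first to second dose, F the share vaccinated by tau, and m the mean day of receipt among those vaccinated by tau. Without censoring before tau:

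- RMST(tau) = E[min(T, tau)] = F x m + (1 - F) x tau
- RMST(tau) - m = (1 - F) x (tau - m)

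The difference is zero only if F = 1 or m = tau. Whenever some but not all children are vaccinated before tau, RMST(tau) is later than m. That direction needs no assumption about the size of F or m.

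**Inputs.** Tau = 42 is from SAP 2.3.5 and 2.3.5.1. The earliest valid second dose is day 28 (Background: at least four weeks apart; the text-message schedule also treats day 28 as the due day). The documents give neither F nor m at day 42, so both are assumed. The Background's 40-60% is season-long and from earlier studies. For the same children, uptake by day 42 cannot exceed uptake by the end of the season, so it serves as a rough upper guide.

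**Results at tau = 42:**

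| F by day 42 (assumed) | RMST if m = 28 | gap to m | RMST if m = 35 | gap to m |
|---|---|---|---|---|
| 0.2 | 39.2 | 11.2 | 40.6 | 5.6 |
| 0.4 | 36.4 | 8.4 | 39.2 | 4.2 |
| 0.6 | 33.6 | 5.6 | 37.8 | 2.8 |
| 1.0 | 28.0 | 0 | 35.0 | 0 |

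**What the sentence would report.** Take F = 0.4 and m = 35: 0.4 x 35 + 0.6 x 42 = 14.0 + 25.2 = 39.2. The SAP's sentence becomes a claim that children receive the dose on average by day 39.2. But 60% have no second dose by day 42. If doses fall evenly over days 28 to 42, the share vaccinated by day 39.2 is 0.4 x (39.2 - 28)/14 = 32%.

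**Uptake and timing are mixed.** 25% vaccinated, all on day 28: 0.25 x 28 + 0.75 x 42 = 38.5. 50% vaccinated, all on day 35: 0.50 x 35 + 0.50 x 42 = 38.5. The value is the same with half the uptake and doses a week earlier, so the number cannot be read as a date.

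**Limit on the direction.** The result that RMST is later applies to children vaccinated by tau. For all children vaccinated by April 30 the sign can reverse. Assume 40% vaccinated by day 42 at mean day 33 and a further 20% later at mean day 80. RMST(42) = 0.4 x 33 + 0.6 x 42 = 38.4. The mean day among all vaccinated is (0.4 x 33 + 0.2 x 80)/0.6 = 48.7, so here RMST(42) is about 10 days earlier.

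**Censoring.** Section 2.3.5 reports that 84-90% "of children has observation windows that extended to day 90 from date of first dose", so 10-16% do not reach day 90. The Kaplan-Meier estimate underlying RMST handles these children, and the meaning of the quantity does not change.

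**The case against.** The best defence is that the paragraph already contains the correct definition, that its opening condition about following children for 42 days signals the restriction, and that the plan supplies what a careful reader needs: inverted Kaplan-Meier curves (2.3.2) and completion differences at days 42, 60 and 90 (2.3.4), the same times as tau. RMST is also described as another way of reporting the data. This stands as a limit on the harm. It does not rescue the sentence. The correct definition is offered as the theoretical alternative and the plain reading is not withdrawn. Restricting follow-up also does not turn 42 days without a dose into a day of receipt.

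Four stronger readings are tempting, and the documents do not support them.

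- A reader might infer that the SAP calls the between-arm RMST difference a shift in the date of vaccination. It says only that such differences can be estimated.
- A reader might infer that day X is always later than the mean day among vaccinated children. That holds only for those vaccinated by tau, as the 38.4 against 48.7 example shows. Nor does the SAP name either mean as its target, so the gaps in the table measure distance from a natural reading of the sentence, not from a stated estimand.
- A reader might take section 3.1.1's condition, "assuming that the outcome will lie in the probability range of 0.2 and 0.8", as a forecast of uptake by day 42. It is a working condition for a linear subgroup model of the binary outcome. It agrees with incomplete uptake but is not a day-42 input.
- A reader might want a fixed uptake threshold above which the sentence becomes acceptable, especially at tau 60 and 90. Any such figure depends on an assumed mean dose day and a chosen tolerance, and the documents give neither.

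**Conclusion.** The sentence is wrong as written, and the error is minor. RMST(tau) is mean days without a second dose in the first tau days. It can be read as a mean day of receipt only if essentially all children are vaccinated by tau, which the 40-60% season-long completion makes implausible at day 42.

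Over assumed uptake of 40-60% by day 42 and an assumed mean day of 28 to 35, RMST(42) is 2.8 to 8.4 days later than the mean day among those vaccinated by day 42. These sizes rest on assumed uptake and timing with no censoring before day 42. The definition and the direction relative to children vaccinated by tau do not depend on those assumed values. Against all children vaccinated by April 30, RMST may be earlier or later.

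The estimator, the curves, the risk differences and the primary outcome are not affected. Only the interpretation of a non-primary Aim 2 analysis is.

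**What to change.** Replace the interpretive sentence in section 2.3.5 with:

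> RMST(tau) is the mean number of days without a second dose during the first tau days after dose 1; children followed to tau without a second dose contribute tau days, and children censored on April 30 before tau are handled through the Kaplan-Meier estimate. The between-arm difference is the mean difference in days without a second dose over the first tau days.

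Use this label at tau 42, 60 and 90 and for any RMST subgroup results under section 3.2. The cost is one SAP sentence, entered as a dated amendment, and the table labels. No new data, code or analysis is needed.
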